### Limitations

It is possible that there may be a limitation in the age range of the sample size, as we are recruiting from a university setting. There are no other known limitations to the present study.

### Implications

This study will provide researchers and clinicians with the data to compare disordered populations with normative parameters across clinical testing procedures. The results will contribute to evidence for identifying disorder and subsequently recommending certain swallowing therapy approaches.

None of the study members on this team have a financial interest or conflict of interest.

Title: Establishing Normal Swallowing and Breathing Profiles in Healthy adults across the age span

NCT: 03122145

Date: March 1, 2019

Experiment #1: Statistical Analysis Plan

Table 1. Test domains and corresponding outcome variables.

Domain	Test	Outcome Variable
Cough	Reflexive cough testing: Capsaicin: (0,50,100,150,200uM) Suprathresholds: Capsaicin: 200uM	-Motor threshold: cough total (ordinal) -Sensory threshold: Urge-to-cough rating (ordinal) -Log transformed Urge-to-cough sensitivity slopes (continuous) -Motor: peak expiratory cough flow (continuous)

Table 2. Specific aims, associated measurements and apriori statistical analyses

Aim		Design	Measurement	Apriori Analysis
1	Reflex cough thresholds	Between group comparison	Sensory and Motor Reflex cough thresholds (ordinal)	Mann-Whitney U test comparing reflex cough thresholds of ALS individuals vs. age/gender matched healthy controls
2	Dose-dependent response curves	Between group comparison	Urge to cough sensitivity (continuous)	A slope calculated by plotting the UTC ratings against capsaicin concentration on a log-log scale, and fitting a linear regression line to the data. Comparisons between ALS vs. controls
3	Voluntary cough	Between group	Peak expiratory cough flow	Mann Whitney U between groups comparison for voluntary cough parameters between healthy controls and individuals with ALS outcomes: peak expiratory cough flow

Experiment #2: Statistical Analysis Plan

For Laryngeal Vestibule Closure (LVC) timing measures, a linear mixed effects model was used to compare the duration of LVC and duration to LVC among the swallow conditions. Pairwise comparisons were used when fixed effects were significant (Sidak corrected). Outcomes from both analyses were significant at $p \leq .05$. Interrater reliability (20% of the data) and intrarater reliability (5% of the data) for the timing of LVC measures were analyzed using single-measure intraclass correlation coefficients (ICCs). ICC estimates and their 95% confidence intervals were calculated with a consistency of agreement definition. All samples were randomly selected for reliability.

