### Background and Significance

The prevalence of dysphagia may be as high as 22% in individuals over 50 years of age (Howden, 2004). There are few therapeutic options and minimal management strategies offered to treat these individuals and improve sequelae of dysphagia.

Dysphagia contributes to malnutrition, aspiration, pneumonia, reduced quality of life and increased mortality in neurodegenerative disease such as ALS (Tabor et al 2016, Chen, 2005; Burkhead, 2014). One reason for this is the lack of normative data across various measures of swallowing and respiratory function. As a result, detecting early impairments in swallowing physiology is difficult, given the variability of swallowing and unknown normative value range of swallowing physiology. Therefore, the goal of this study is to complete clinical tests of swallowing and cough function in healthy volunteers to establish normative data. This will contribute to future study in disordered populations, to determine degree and severity of impairment and efficacious treatment and management strategies based on impairment.

Purpose: The purpose of this study is to establish normative values for clinical testing measures of swallow, respiratory and cough functions. This will aide in establishing degree of impairment in disordered populations, and in identifying efficacious treatment paradigms for dysphagia.

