### Population and Sampling Data

Participants will include up to 120 adults, both males and females across the lifespan. The primary goal of the proposed study is to establish normative data for comparison

with disordered dysphagic populations in an age and gender matched fashion. This study represents a pilot study and the work proposed and comparisons planned have not yet been performed in the dysphagic population using clinical testing measurements. Given that some volunteers may not be able to complete all required tasks and lead to missing data we will recruit and run 20% additional than our target number of 100 for a total of 120 participants. drop and some data may not be included, we plan to study approximately 100 participants. A power analysis is not included in the protocol as we are conducting the first study to collect normative data and establish a database of 'normal' functioning across various swallow and respiratory parameters.

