#### Inclusion/Exclusion Criteria.

A total of 120 individuals will be included in this study. Subjects will include both male and females who are aged between 18-100, healthy and with no major medical conditions. Adults who are pregnant, or those with major medical conditions (i.e., swallowing impairment, brain injury) will be excluded from this study. Anyone with allergy to barium will be excluded from this study. No specific gender or race will be excluded or targeted for participation in this study.

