#### Cough

*Voluntary Cough Testing:*

Voluntary cough function will be assessed using an oral pneumotachograph (MLT 1000, ADInstruments, Inc; Colorado Springs, CO), connected to a spirometer filter (MQ 304 Spirometer Filter, Vacumed; Ventura, CA) during voluntary cough production. The participant will be seated with a respiratory facemask held in place by the examiner and instructed to complete three tidal breaths into the facemask, take a deep breath in and then “cough hard like you have something stuck in your throat”. This task will be modeled to the patient by the examiner and practiced first to ensure the patient understands the procedure. Airflow signal will be measured, low pass filtered at 150Hz, digitized at 1 KHz and displayed on a portable laptop computer using Chart Version 7 (Microsoft Corp; Redmond, WA).

*Reflexive Cough Testing:*

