### Data Analysis

Data analysis will be primarily descriptive, including central tendency, range and standard deviation in order to determine average values for each of the completed tests. This will help to create the database for normative parameters for swallowing and respiratory tasks.

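### All three SAP Experiment 1 aims compare ALS with healthy controls, but the protocol enrols only healthy adults and neither document defines an ALS group

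*SAP*

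**What the plan says.** SAP, Experiment #1, Table 2 lists three aims, each a between-group comparison. Aim 1 (reflex cough thresholds, ordinal) is a "Mann-Whitney U test comparing reflex cough thresholds of ALS individuals vs. age/gender matched healthy controls". Aim 2 (urge-to-cough slope, continuous) compares ALS with controls and names no test. Aim 3 (voluntary peak expiratory cough flow) is a Mann-Whitney comparison of healthy controls and people with ALS. Only Aim 1 says that the controls are matched.

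The protocol, Inclusion/Exclusion Criteria, states: "Subjects will include both male and females who are aged between 18-100, healthy and with no major medical conditions". It excludes people with major medical conditions and gives swallowing impairment as an example.

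On disordered groups the protocol points two ways. Population and Sampling Data says that the norms are for comparison "with disordered dysphagic populations in an age and gender matched fashion", and adds that "the work proposed and comparisons planned have not yet been performed in the dysphagic population using clinical testing measurements". Background and Significance says of the norms: "This will contribute to future study in disordered populations". On size, Population and Sampling Data says: "A power analysis is not included in the protocol as we are conducting the first study to collect normative data".

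The protocol's Data Analysis section plans a mainly descriptive analysis: "central tendency, range and standard deviation in order to determine average values for each of the completed tests". The SAP has no such summary. Its Experiment #2 is a mixed model of laryngeal closure timing across swallow conditions, with reliability coefficients.

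**The concern.** An analysis plan should be executable on the data that the study collects. Here every pre-specified test in Experiment 1 needs a group that the protocol does not recruit. If an ALS group is brought in from elsewhere, nothing fixes in advance who belongs to it, how many there are, how they were tested or how controls are chosen for them. Those choices could then be made after the data are seen.

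The reason given for having no power analysis, that the study collects norms, does not extend to three hypothesis tests.

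Comparability of testing also matters. In Aims 1 and 2 the capsaicin series fixes which threshold levels can be observed and the points through which the slope is fitted. ALS participants tested with another series could differ from controls for that reason alone. Aim 3 does not have this problem, since "Voluntary cough function will be assessed using an oral pneumotachograph" and no capsaicin is given. There the apparatus, the instructions, age and sex are what must be comparable.

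**Working it through.** **1. The plan's own figure.** The only sample-size figure is the recruitment total in Population and Sampling Data: a target of 100 plus 20%, so 100 × 1.20 = 120. It reproduces. All 120 are healthy adults. No size, effect or power is given for any ALS contrast, so there is no comparative figure to reproduce.

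**2. Aims against enrolment.**

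| Aim | Outcome | Test named | Matching stated | ALS size stated | ALS participants enrolled |
|---|---|---|---|---|---|
| 1 | Reflex cough thresholds | Mann-Whitney U | Yes, method not given | No | 0 |
| 2 | Urge-to-cough slope | None | No | No | 0 |
| 3 | Voluntary peak cough flow | Mann-Whitney U | No | No | 0 |

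So 3 of 3 contrasts lack one of their two groups.

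**3. Norms against SAP.** The protocol's Outcome Measures section lists MEP/MIP, high resolution manometry, swallow timing and kinematics, and tongue pressure. Cough is not in that list but is in the stated purpose. The SAP does not mention MEP/MIP, manometry or tongue pressure. It treats swallow timing only as a comparison between conditions, and cough only as ALS against controls. It gives descriptive norms for none of them.

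**4. What the missing size is worth, Aim 3 only.** Assumptions: normal continuous data, two-sided alpha 0.05, 80% power, Mann-Whitney efficiency 3/π = 0.955 relative to the t-test, and 100 analysed healthy adults (the protocol's target). The ALS sizes nA are assumed, because the documents give none. With nC controls:

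detectable difference in SD = (1.96 + 0.84) / √(0.955 × nA × nC / (nA + nC))

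For nA = 20 and nC = 100: 0.955 × 2000/120 = 15.92, whose square root is 3.99, and 2.80/3.99 = 0.70. For 20 against 20: 0.955 × 400/40 = 9.55, whose square root is 3.09, and 2.80/3.09 = 0.91.

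| ALS n | Against 100 controls | 1:1 matched |
|---|---|---|
| 10 | 0.95 SD | 1.28 SD |
| 20 | 0.70 SD | 0.91 SD |
| 30 | 0.60 SD | 0.74 SD |
| 50 | 0.50 SD | 0.57 SD |

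The documents give no SD for peak flow, so these cannot be turned into flow units.

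**5. Why the table stops at Aim 3.** Aim 1 is ordinal, with few levels and many ties. A simulation of 20 against 100 with a latent shift of 0.70 SD, on an assumed scale of 4 to 5 evenly filled levels, gave about 76% power rather than 80%. Scales with a floor gave 52% to 72%. Aim 2 names no test, so no formula can be assigned to it.

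**6. Capsaicin series.** The protocol's Reflexive Cough Testing section lists 0, 50, 100, 200 and 500 µM. SAP Table 1 lists 0, 50, 100, 150 and 200 µM. The two share 0, 50, 100 and 200, which is 4 of 6 distinct concentrations.

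**The case against.** The best defence is that the comparison is foreseen. The protocol gives matched comparison with dysphagic populations as the use of the norms and refers to planned comparisons, so the healthy adults may be meant as controls for an ALS cohort studied elsewhere. That is a fair reading. It means that the contrasts are not foreign to the project and that they may be feasible with outside data. It does not supply the dataset, its size or the matching rule, and Background and Significance leaves disordered populations to later work.

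Four stronger readings are tempting and are not supported:

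- A reader might infer that the study's normative purpose has been lost. It has not. The protocol's Data Analysis section still covers each completed test; what is missing is its transfer into the SAP.
- A reader might infer that Experiment 1 can never be completed. That holds only for the study's own participants; the documents do not settle whether a companion ALS dataset exists.
- A reader might infer that Aims 2 and 3 would produce inflated false positives from an age imbalance. The documents give no age gap, and if these aims use Aim 1's matched controls, the natural reading, the rate stays near 5%.
- A reader might take the two capsaicin series as evidence that ALS participants and controls were tested differently. The mismatch is between protocol and SAP within one study; it says nothing about what any ALS group received.

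**Conclusion.** The point stands in a limited form. As written, none of the three Experiment 1 contrasts can be run on the participants whom this protocol enrols, and the SAP does not contain the descriptive analysis that these participants can support. This rests on the text alone and needs no assumption.

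The detectable differences only show scale. They apply to Aim 3 under normal continuous data and assumed ALS sizes. Across 10 to 50 ALS participants they run from 0.95 down to 0.50 SD with 100 controls, and from 1.28 down to 0.57 SD with 1:1 matching. Both the size and the matching method therefore matter, and neither is stated. A reader might carry these figures over to Aim 1, but an ordinal outcome would do worse. The point should be corrected before Experiment 1 is analysed or reported under this SAP.

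**What to change.** 1. **Make the norms the main SAP analysis.** Carry the protocol's descriptive analysis into the SAP for healthy participants: centre, range and SD for continuous measures; median, range and level frequencies for ordinal thresholds. Cover the cough variables and the Outcome Measures list (MEP/MIP, manometry, swallow timing and kinematics, tongue pressure). Percentiles with confidence intervals and age-and-sex regression are optional additions that the protocol does not ask for.
2. **Remove or define the ALS contrasts.** If they are kept, label them secondary comparisons with a named external ALS dataset, and state its eligibility, size, test procedures and matching method. For Aims 1 and 2, the ALS group should have been tested with the same capsaicin series as the controls. For Aim 3, it should have had the same voluntary-cough apparatus and instructions.
3. **Treat age and sex alike in all three aims.** Either use one matched control set with Mann-Whitney U throughout, including the Aim 2 slopes, or use age- and sex-adjusted models (proportional odds for thresholds, linear for slopes and peak flow).
4. **Reconcile the documents.** The capsaicin series in the protocol and SAP Table 1 must be brought into agreement. Table 1, in the text available, lists peak cough flow only under reflexive testing, so it should be reconciled with Aim 3's voluntary cough.

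The cost is SAP wording and minor analysis work, with no extra healthy participants. An external comparison supports weaker claims than a concurrent one, and Aims 1 and 2 may lose ALS participants who were tested with another series.

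### Aim 1 matches controls to ALS individuals on age and gender but tests the thresholds unpaired and unadjusted, which is conservative and loses power if either factor predicts the threshold

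*SAP*

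**What the plan says.** In SAP Experiment #1, Table 2, the Aim 1 row plans a "Mann-Whitney U test comparing reflex cough thresholds" of "ALS individuals vs. age/gender matched healthy controls". The design column describes this as a comparison between groups, and the thresholds are classed as ordinal. The Protocol, Population and Sampling Data, gives the same intent in general terms: normative data to be compared "with disordered dysphagic populations in an age and gender matched fashion".

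Neither document says whether matching is by individual or by group, or gives the ratio, the age tolerance or the number of ALS individuals. Neither plans a paired, stratified or age- and gender-adjusted analysis for Experiment #1.

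Aim 3 uses a "Mann Whitney U between groups comparison for voluntary cough parameters between healthy controls and individuals with ALS" and does not mention matching. Aim 2 compares slopes between ALS and controls but names no test.

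**The concern.** Matching on a factor that predicts the outcome makes the two groups more alike than two independent samples would be. The Mann-Whitney test takes its null variance from independent samples, so it overstates the chance variation in the group difference. The design uses age and gender and the analysis then sets them aside.

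What is at stake is a missed difference, not a false one. That matters here because nothing shows that the comparison has power to spare. The Protocol says "A power analysis is not included in the protocol", and the ALS sample size appears nowhere.

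**Working it through.** **Figures in the documents.** The only sample-size figure is for healthy volunteers: "we will recruit and run 20% additional than our target number of 100 for a total of 120 participants". It reproduces, since 100 × 1.20 = 120, but it is not specific to the ALS comparison. No power, effect size or SD is given for Aim 1. The 0.05 level is stated only under Experiment #2, so two-sided 0.05 is assumed for Experiment #1.

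**Assumptions.** These are 30 per group, a five-level ordinal outcome with equal null frequencies, and a shift of 0.6 SD on the underlying normal scale. The correlation ρ between matched subjects is varied over 0, 0.1, 0.3 and 0.5. With exact matching, ρ is the share of outcome variance due to age and gender; looser matching lowers it.

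**Step 1: large-sample level.** With n matched per group, the variance of the group difference is 2σ²(1−ρ)/n, whereas the unpaired test assumes 2σ²/n. The test statistic therefore has SD √(1−ρ) under the null, and

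true α = 2Φ(−1.96/√(1−ρ)).

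- ρ = 0: 2Φ(−1.96) = 0.050
- ρ = 0.1: 2Φ(−1.96/0.949) = 2Φ(−2.07) = 0.039
- ρ = 0.3: 2Φ(−1.96/0.837) = 2Φ(−2.34) = 0.019
- ρ = 0.5: 2Φ(−1.96/0.707) = 2Φ(−2.77) = 0.006

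**Step 2: simulation on the ordinal scale.** The comparator is a regression of the ranks on group and the matching covariate.

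| ρ | True α, Mann-Whitney | Power, Mann-Whitney | Power, adjusted |
|---|---|---|---|
| 0 | about 5% | 57% | 58% |
| 0.1 | 3.7% | 57% | 61% |
| 0.3 | 2.0% | 59% | 71% |
| 0.5 | 1.0% | 61% | 83% |

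The power differences are 1, 4, 12 and 22 points. The 1 point at ρ = 0 is within simulation noise. I repeated this run and obtained the same pattern, to within about two points of power. The model is given the shared component exactly, as one linear covariate. Coarser coding of age and gender would recover less, so the gains are near a best case for each ρ.

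**Step 3: does it depend on individual pairs?** No. With two groups of 30 sharing the same age distribution but analysed without pair links (continuous outcome, shift 2.8 × √(2/30) = 0.72 SD), the simulated Mann-Whitney level is 0.043 when age explains 10% of the variance and 0.016 when it explains 30%. Power against adjusted rank regression is 76% vs 76%, 78% vs 81% and 79% vs 90% at 0%, 10% and 30% explained.

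**Step 4: is the signed-rank test the natural replacement?** Not by default. In a separate run at the Step 2 settings with 1:1 pairs, power for Mann-Whitney versus signed-rank was 59% vs 57% at ρ = 0, 57% vs 59% at 0.1, 56% vs 67% at 0.3 and 59% vs 80% at 0.5. Between 20% and 33% of pairs were tied at zero.

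**The case against.** The strongest reply is that the Mann-Whitney choice is defensible. Table 2 describes a comparison between groups, and no text sets up pairs. Under frequency matching, an independent-groups test is not the wrong class of test. Matching also balances age and gender as confounders, and the unpaired test keeps that benefit. A significant result stays valid. At a correlation of 0.1 or less the loss is only a few points. All of this stands, and it limits the severity.

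It does not remove the point. Step 3 shows the same conservatism without pairs, and adjustment costs essentially nothing at zero correlation.

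A reader might go further in four ways that the documents do not support:

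- That the controls are individually paired, so that an independent-samples test is invalid. Neither document states 1:1 matching.
- That the error rates are certainly wrong and power certainly lower. Both depend on a correlation that is not given.
- That reported intervals would be too wide. Experiment #1 specifies no intervals.
- That match identifiers already exist. The Protocol's eligibility criteria cover healthy volunteers only, and neither document mentions a match identifier. Matching does, however, require age and gender to be known in both groups, and adjustment needs nothing more.

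**Conclusion.** The point holds in conditional form. As written, Aim 1 discards the factors used to choose its controls. If age or gender predicts the threshold, the planned test is conservative and loses power.

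The size is negligible to modest at low correlation and substantial at 0.3 to 0.5. Those correlations, the 30 per group, the five levels and the 0.6 SD shift are all assumptions, because the documents supply none of them. Simulations of matched pairs at 20 and 50 show the same direction. There is no excess of false positives.

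This is a free improvement of low-to-moderate severity. The extension to Aims 2 and 3 is conditional, because those rows do not say that matched controls are used.

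**What to change.** - State the matching method, ratio, age tolerance and number of ALS individuals in the SAP.
- Make the Aim 1 analysis a proportional-odds or rank-based model with group, age and gender, or a van Elteren test stratified by gender and age band. Either suits pair or frequency matching and keeps unmatched participants.
- Use a paired analysis only if matching is 1:1 and identifiers are kept. Note in the SAP that signed-rank ranks the sizes of differences, which ordinal levels do not strictly support, that it handles ties poorly, and that it is slightly less powerful when the correlation is near zero.
- If the same matched controls serve Aims 2 and 3, apply the same adjustment to the urge-to-cough slopes and to peak expiratory cough flow, and name the Aim 2 test.
- If Aim 1 has already been analysed, report the adjusted result as a labelled supplementary analysis.

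The cost is SAP wording and one more model. The variables are those that matching already requires. The proportional-odds form adds an assumption to check, and in a small sample the age bands for van Elteren should be few.
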